20. Serum samples for measurement of sUA levels will be collected at the Screening Visit, the Week -6 Visit (prior to the first dose of MTX), the Week -4 Visit (Randomization) and the Week -2 Visit during the Run-in Period. On Day 1, a pre-infusion and post infusion sUA will be collected to be shipped to the Central laboratory. For the remainder of study visits beginning at Week 2 during the Pegloticase +IMM period; 2 Serum Uric Acid samples will be collected within 48 hours PRIOR to each pegloticase infusion until Week 24 visit. After Week 24, if a subject's previous visit sUA (local or central laboratory) is less than 6 mg/dl; it will be allowable to draw the local pre-infusion sUA sample on the same day and similar time as the sample to send to the central laboratory; however, if the prior visit sUA sample was greater than 6 mg/dl (local or central laboratory), a local sUA sample will need to be collected and read out prior to the pegloticase infusion to be certain the subject has not met the stopping rule. One sample will be for testing at the site's local laboratory for sUA levels and the second sample will be sent to the Central Laboratory. A POST infusion sUA blood sample will additionally be collected on Day 1, and at the Weeks 2, 6, 10, 12, 14, 20, 22, 24, 32, 34, 36, 48 and 50 for same day shipment to the Central Laboratory. Additional serum samples for sUA levels will be collected at non-infusion Visits at Weeks 21 and 23 and the End of Pegloticase Infusions Visit (if applicable) and the Week 52/End of study/Early Termination Visit and 3 and 6 month Follow-up Visits. Subjects with an sUA level  $>6$  mg/dL at 2 consecutive study visits beginning with the Week 2 Visit will discontinue pegloticase and complete the End of Pegloticase Infusions Visit (if applicable) or the Week 52/End of study/Early Termination Visit. See the Laboratory Manual for instructions for alternate scenarios. In the event of an AE suspected to be an infusion reaction, a serum sample will be collected at that time or at the subsequent visit for evaluation of pegloticase antibodies.
21. Serum samples for evaluation of anti-PEG and anti-uricase IgG antibodies will be collected prior to the pegloticase infusion on Day 1 and at the Weeks 2, 6, 14, 22, 24, 36; and at the non-infusion End of Pegloticase Infusions Visit (if applicable) or the Week 52/End of Study/Early Termination Visit and Month 3 Post Treatment Follow-up Visits.

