All subjects who complete the Run-In Period will receive the first pegloticase infusion on Day 1. All subsequent doses and study visits will be scheduled based on the Day 1 visit date.

It is required that before a subject begins the pegloticase + IMM Period, he or she has been taking at least one protocol standard gout flare prophylaxis regimen (i.e. colchicine and/or non-steroidal anti-inflammatory drugs and/or low-dose prednisone  $\leq 10$  mg/day) for  $\geq 1$  week before the first dose of pegloticase and continues flare prophylaxis per American College of Rheumatology guidelines [Khanna D et al. 2012] for the greater of 1) 6 months, 2) 3 months after achieving target serum urate (sUA  $< 6$  mg/dL) for patients with no tophi detected on physical exam, or 3) 6 months after achieving target serum urate (sUA  $< 5$  mg/dL) for patients with one or more tophi detected on initial physical exam that have since resolved. For IR prophylaxis, fexofenadine (180 mg orally) will be taken the day before each infusion; fexofenadine (180 mg orally) and acetaminophen (1000 mg orally) will be taken the morning of each infusion; and methylprednisolone (125 mg IV) given over an infusion duration between 10 - 30 minutes, immediately prior to each infusion.

During the Pegloticase + IMM Period, pegloticase 8 mg will be administered intravenously (IV) every 2 weeks from Day 1 through the Week 50 Visit for a total of 26 infusions; pegloticase will be administered after all pre-dose study visit assessments have been completed at each visit. The date and start and stop time of infusion will be recorded. Serum uric acid stopping rules will be applied: subjects with sUA level  $> 6$  mg/dL at 2 consecutive study visits beginning with the Week 2 Visit will discontinue treatment, complete the End of Pegloticase Infusion Visit procedures within 2 weeks and continue the subject visits according to the protocol (without treatment).

During the Pegloticase + IMM Period, subjects will be instructed to take MTX or placebo for MTX weekly on the same day each week, within 1 to 3 days prior to each pegloticase infusion and one additional weekly dose after the last infusion for subjects who have not stopped pegloticase due to sUA stopping rules; however, if a subject does not do so, MTX or placebo for MTX must be taken  $\geq 60$  minutes prior to each pegloticase infusion.

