- Record vital signs (blood pressure, respiratory rate, temperature, and heart rate) prior to the pegloticase infusion and any time after the end of the infusion, but prior to discharge. (See [Section 9.5.4.4](#)). During the pre-infusion blood pressure collection, at sites who participate and from subjects who consent, optional intensive BP collections will be obtained. For this optional collection, three blood pressure measurements should be

performed, at least 2 minutes apart, with BP readings measured to the nearest mm Hg prior to pegloticase infusion. If any of the 3 systolic blood pressure measurements differed by more than 8 mm Hg or if diastolic measurements differed by more than 5 mm Hg, repeat sets of 3 sitting blood pressure measurements will be obtained until the difference is less than 8 mm Hg for systolic and less than 5 mm Hg for diastolic.

- Assess MTX/placebo for MTX compliance and re-dispense MTX/placebo for MTX.
- Ask Yes/No question regarding folic acid, gout flare prophylaxis, and IR prophylaxis compliance.
- Fill gout prophylaxis, fexofenadine, acetaminophen, and folic acid prescriptions, as needed.
- Obtain a urine sample from all females of childbearing potential for performance of a pregnancy test.
- Administer IR prophylaxis (i.e., fexofenadine, acetaminophen, and methylprednisolone) (see [Section 9.4.1.3](#)).
- Administer pegloticase and record date, volume, and duration of infusion, and start/stop (inclusive of 10-mL flush) times of dosing.
- Inquire about AEs and concomitant medication use.

#### 9.5.8.2.11 Week 20

- Obtain 2 blood samples for measurement of sUA within 48 hours prior to the pegloticase infusion at this visit. One sample will be tested for sUA at the site's Local Laboratory and one sample will be shipped to the Central Laboratory for testing. The Local Laboratory or Central Laboratory pre-infusion sUA results should be reported prior to pegloticase infusion. To note: It is allowable for the Local and Central Laboratory sUA samples to be drawn on different days or times so long as both samples are drawn within 48 hours prior to the infusion and the results of at least one sample are available prior to the infusion. (see [Section 9.5.1.1](#)).
  - Stopping rule: Subjects with an sUA level  $>6$  mg/dL at 2 consecutive study visits beginning with the Week 2 Visit (not including post-infusion samples) will subsequently discontinue treatment and remain in the study.

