#### **9.6.5.1 Primary and Secondary Endpoint Analysis**

The primary analysis will be conducted in the ITT population. The primary efficacy endpoint is the proportion of responders during Month 6. A responder is defined as a subject for whom the proportion of time that the sUA-time curve is <6 mg/dL during the analysis interval is at least 80%. The proportion of time that the sUA level is below 6 mg/dL is defined as the ratio of the time during which the sUA level remains below 6 mg/dL (using linear interpolation, if necessary) to the entire time interval during Month 6. A subject will be declared a non-responder if the subject had 2 sUA levels >6 mg/dL at 2 consecutive study visits beginning with the Week 2 Visit prior to or during Month 6. Additionally, a subject who withdraws from study treatment for any reason other than the stopping rule after randomization and prior to or during Month 6 (for the primary endpoint) or Months 12 (for the secondary endpoint) will be considered a non-responder at the time of withdrawal (and for all subsequent time points) if sUA values are not collected at the planned time points. Sensitivity analyses of the primary and secondary endpoints will include data (if available) for subjects who discontinue treatment due to stopping rule and remain on study. Special consideration may be given to subjects who discontinue the study or miss visits due to reasons related to the COVID-19 pandemic.

The analysis of the primary endpoint and the secondary responder endpoints will assess risk difference (difference in response proportions) in a stratified analysis. The analysis will use Cochran-Mantel-Haenszel (CMH) weighting to estimate the common risk difference within strata and to estimate the standard error of the common risk difference. Stratification for the analysis will use the same factor as was used to stratify randomization, presence of tophi (yes, no). The difference in response rates, comparing pegloticase with MTX vs. pegloticase with placebo for MTX, will be estimated along with the corresponding 95% confidence interval (CI) and p-value.

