## **9. Efficacy**

### **9.1. Handling Rules for sUA Values**

Serum samples for measurement of sUA levels are scheduled for collection at the Screening Visit, the Week -6 Visit (prior to the first dose of MTX), the Week -4 Visit (Randomization) and the Week -2 Visit during the Run-in Period; On Day 1, a pre-dose and post dose sUA will be collected to be shipped to the Central laboratory. For the remainder of study visits beginning at Week 2 during the Pegloticase + IMM period, 2 Serum Uric Acid samples will be collected within 48 hours PRIOR to each pegloticase infusion. One sample will be for testing at the site's local laboratory for sUA levels and the second sample will be sent to the Central Laboratory. A post-infusion sUA blood sample will additionally be collected on Day 1, and at the Weeks 2, 6, 10, 12, 14, 20, 22, 24, 32, 34, 36, 48 and 50 for same day shipment to the Central Laboratory. Additional serum samples for sUA levels are collected at non-infusion Visits at Weeks 21 and 23 and the End of Pegloticase Infusions Visit (if applicable) and the Week 52/End of study/Early Termination Visit and 3 and 6 month Follow-up Visits. Subjects with an sUA level >6 mg/dL at 2 consecutive study visits beginning with the Week 2 Visit will discontinue pegloticase and complete the End of Pegloticase Infusions Visit (if applicable) or the Week 52/End of study/Early Termination Visit procedures.

- For the determination of sUA responder endpoints, scheduled assessments of sUA and unscheduled assessments of sUA, reported by the central laboratory, will be used. Local laboratory-processed pre-infusion sUA results will be used only when the central laboratory-processed value at a time point is not available, but the local lab-processed pre-infusion value, collected value at the same time point, is available.
- When the central laboratory or local laboratory reports a value for sUA as being lower than the lab assay's limit of quantification (e.g. "<0.02"), zero will be used as the numeric value for the purpose of determining response and for summaries of observed values and the change from baseline.

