#### **9.2.1. Calculation of Response**

The sUA concentrations vs. time (collected to the nearest minute in the CRF) curve will be used to estimate the proportion of time that the sUA is < 6 mg/dL using the available pre-infusion (or values at visit when no infusion performed) and post-infusion samples with non-missing sUA values.

The Month 6 period will include pre-infusion and post-infusion results at Week 20, results at Week 21, pre-infusion and post-infusion results at Week 22, results at Week 23, and pre-infusion results at Week 24, and unscheduled assessments of sUA collected between Week 20 and Week 24

This document is confidential.

processed by the central laboratory. Results from visits where an infusion was not performed (e.g. subject discontinued pegloticase but remained in study) will be used when available. Section 9.1 shows the rules for inclusion of sUA values reported by local laboratories.

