### **9.3. Secondary Efficacy Endpoints and Analyses**

#### **9.3.1. Proportion of Month 12 Responders**

The proportion of Month 12 (Weeks 48, 50, and 52) responders, will be defined as subjects achieving and maintaining sUA < 6 mg/dL for at least 80% of the time during Month 12.

This endpoint will be analyzed for the ITT and mITT populations.

This determination will be completed using the same linear interpolation method described for the primary efficacy endpoint in Section 9.2.1. The Month 12 period will include pre-infusion and post-infusion results at Week 48, pre-infusion and post-infusion results at Week 50, pre-infusion results at Week 52, and unscheduled assessments of sUA collected between Week 48 and Week 52 processed by the central laboratory. Section 9.1 shows the rules for inclusion of sUA values reported by local laboratories.

If the subject's proportion of hours where sUA was less than 6 mg/dL, P, is greater than or equal to 80% the subject will be called a responder for the Month 12 responder endpoint. Subjects meeting the stopping rule, i.e. has pre-infusion sUA values greater than 6 mg/dL at 2 consecutive scheduled visits (starting at Week 2) through Week 52 will be counted as non-responders. A subject with the proportion of hours, P, less than 80% will be counted as non-responders.

There will be no imputation of sUA values due to missing values among those collected between Week 48 and Week 52, unless missing data is due to "Site Closure". At least two sUA observations from different visits must be available in order for a subject to be eligible for consideration as a responder. Subjects with only one sUA observation will be considered a non-responder, regardless of the value of that single observation. For subjects with "Site Closure" missing data (as defined in Section 6.3.3) during Month 12, the rules described in Section 6.3.3 will be applied. The proportion of Month 12 responders will be analyzed using the same multiple imputation method and the stratified weighting approach specified for primary analysis of the primary endpoint.

In addition, the proportion of responders along with a 95% confidence interval for the proportion will be summarized based on the observed data (i.e. with no imputation based on COVID-19 impact), with non-responder imputation used for subjects who meet the stopping rule or have missing results during Month 12 (this will be the primary analysis method if there are no "Site Closure subjects").

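### The responder curve falls from the pre-infusion draw, up to 48 h before the drug is given, so draw time alone can move a subject across the 80% cut

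*Protocol*

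**What the plan says.** - **Draw window.** Protocol 2.1, footnote 20: "2 Serum Uric Acid samples will be collected within 48 hours PRIOR to each pegloticase infusion until Week 24 visit". One sample is local and one central. The infusion-visit instructions from Week 2 on (Protocol 9.5.8.2) let the two be drawn on different days or times "so long as both samples are drawn within 48 hours prior to the infusion".
- **Which value counts.** SAP 9.1: "scheduled assessments of sUA and unscheduled assessments of sUA, reported by the central laboratory, will be used". A local pre-infusion result is used only when the central one is missing.
- **Curve.** SAP 9.2.1: "The sUA concentrations vs. time (collected to the nearest minute in the CRF) curve will be used to estimate the proportion of time". Its Month 6 points are pre- and post-infusion at Weeks 20 and 22, single values at Weeks 21 and 23, and pre-infusion at Week 24. Protocol 9.6.5.1 specifies linear interpolation and an 80% cut. SAP 9.3.1 applies the method to Month 12, "using the same linear interpolation method described for the primary efficacy endpoint in Section 9.2.1".
- **Infusion times.** Protocol 9.1: "The date and start and stop time of infusion will be recorded". No visible rule uses these times in the curve.
- **Related rules.** SAP 9.2.2 makes a subject a non-responder after two consecutive scheduled visits above 6 mg/dL, post-infusion samples excluded. SAP 9.2.4 adds a supplemental analysis in which one such value is enough. None of the five sensitivity analyses in SAP 9.2.5 varies draw timing.

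**The concern.** When the pre-infusion value is above 6 and the post-infusion value is low, the drop is due to the infusion. The interpolated line starts the drop at the blood draw. If the draw was a day or two early, part of that period is scored as below 6 although the dose had not been given.

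The error on this segment always favours response, and it grows with how early the site drew blood, which says nothing about the subject's urate control. Two subjects with the same sUA values can be classified differently. The Month 3, 9 and 12 responder endpoints, the 5 mg/dL versions and the percentage of non-hyperuricemic time use the same construction.

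**Working it through.** **Plan's own figure.** SAP 9.2.2 uses 28 days for Month 6: 28 × 24 = 672 h. Response needs 0.80 × 672 = 537.6 h below 6, which leaves an allowance of 134.4 h.

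**Assumptions (not in the documents).** Post-infusion sUA is 0, sampled 2.5 h after infusion start. A value above 6 does not fall back below 6 between draw and infusion.

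**Credit per infusion.** Let V be the pre-infusion value (above 6) and g the hours from draw to infusion.
- As written, time below 6 on the falling line = (g + 2.5) × 6/V.
- Value held to infusion start = 2.5 × 6/V.
- False credit = 6g/V.

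| g | V = 12 | V = 6.5 | Points of 672 h |
|---|---|---|---|
| 2 h | 1.0 h | 1.8 h | 0.1 to 0.3 |
| 4 h | 2.0 h | 3.7 h | 0.3 to 0.5 |
| 12 h | 6.0 h | 11.1 h | 0.9 to 1.6 |
| 24 h | 12.0 h | 22.2 h | 1.8 to 3.3 |
| 48 h | 24.0 h | 44.3 h | 3.6 to 6.6 |

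With post-infusion sUA of 0.5 to 3 at 2 h and V of 6.5 to 10, a 48 h lead credits 19 to 44 pre-infusion hours, or 2.9 to 6.5 points. Month 6 has two such segments (Weeks 20 and 22), so a subject high at both and below 6 at Week 21 collects the credit twice.

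**Constructed subject.** Weeks 20 to 24 = 2, 5.5, 9, 2, 2, with all pre-infusion samples drawn g hours early. Only one visit exceeds 6, so the stopping rule is not met. Segments away from the Week 22 peak total 501.5 h below 6 in every case. The rising line from Week 21 is below 6 for (6 − 5.5)/(9 − 5.5) = 1/7 of its length. The falling line is below 6 for 6/9 of its length.

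| Rule | Rising | Falling | Total | Share |
|---|---|---|---|---|
| At infusion | 168/7 = 24.0 | 2.5 × 2/3 = 1.7 | 527.2 | 78.4% |
| 12 h early, as written | 156/7 = 22.3 | 14.5 × 2/3 = 9.7 | 533.5 | 79.4% |
| 24 h early, as written | 144/7 = 20.6 | 26.5 × 2/3 = 17.7 | 539.7 | 80.3% |
| 48 h early, as written | 120/7 = 17.1 | 50.5 × 2/3 = 33.7 | 552.3 | 82.2% |
| 24 h early, held | 20.6 | 1.7 | 523.7 | 77.9% |
| 48 h early, held | 17.1 | 1.7 | 520.3 | 77.4% |

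**Month 12.** Weeks 48, 50, 52 = 2, 10, 2, with the first two drawn 48 h early (720 h window): 585.6/720 = 81.3% as written and 556.8/720 = 77.3% held. The gap is 6 × 48/10 = 28.8 h.

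**How often a subject switches.** In 20,000 simulated subjects with an isolated Week 22 excursion (Week 20 = 2; uniform spreads: Week 21 from 2 to 6, Week 22 from 6.05 to 12, Weeks 23 and 24 from 0 to 6), holding the value moves about 1% from responder to non-responder at a 2 h lead, 2% at 4 h, 6% at 12 h, 12% at 24 h and 27% at 48 h. None moves the other way. These rates apply only to subjects with such an excursion.

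**The case against.** Several points limit this.

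- **Existing rules.** The stopping rule removes subjects with consecutive values above 6, and Weeks 21 and 23 are scheduled visits, so mainly isolated excursions remain. SAP 9.2.2 itself expects sUA to stay above 6 once the stopping rule is met. The single-value supplemental analysis makes every affected Month 6 subject a non-responder. That gives a strict bound, but it is a different endpoint and leaves the primary 80%-of-time calculation uncorrected.
- **Early draws are not forced on the endpoint sample.** At the Month 6 infusion visits only one result, local or central, must be available beforehand. A site can draw the local sample early and the central one on the day. After Week 24 the requirement is looser still when the previous value was below 6. A reader might infer that the protocol drives early central draws. It permits them and no more.
- **Unseen material.** Footnote 20 refers to the Laboratory Manual for alternate scenarios, and a figure just before SAP 9.2.1 is not visible. Either could narrow the draw time or the curve rule.
- **A head count.** A reader might multiply an assumed 5 to 10% of subjects with an isolated excursion by 12 to 27% switching and by the 145 planned subjects, giving about 1 to 4. The documents give no source for that prevalence or for draw times. At 2 to 4 h leads the same product is 0.1 to 0.3 subjects.

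All four stand as limits on size. None removes the artefact from the primary calculation.

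**Conclusion.** The point holds as a defect in how the curve is built. An isolated pre-infusion value above 6 earns time below 6 before the drug is given: roughly 2 to 3 points at a 24 h lead, 4 to 7 at 48 h, and well under 1 at 2 to 4 h. This rests on a post-infusion sUA near 0 and no fall before the infusion. Classification near 80% can then depend on draw time. The number of subjects affected cannot be sized and may be near zero if central samples are drawn on the infusion day.

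A reader might infer that the treatment comparison is biased or type I error inflated. The documents do not support that: the rule is identical in both arms, and sites and sponsor are blinded to methotrexate or placebo. What is affected is the absolute response rates and noise in classification. The stated power does not depend on this rule. It is worth correcting because the correction is cheap, but it does not threaten the trial's main conclusion.

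**What to change.** In SAP 9.2.1, and in the sections that reuse the method (9.3.1, 9.4.5 to 9.4.8, 9.4.12), state that the pre-infusion value is held from its sample time to the recorded infusion start, and that linear interpolation to the post-infusion sample begins there. Other segments stay as planned. Specify this before unblinding.

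If the sponsor prefers to leave the primary curve unchanged, add the rule as a sensitivity analysis in SAP 9.2.5 and report draw-to-infusion intervals by arm, so that the reader can see whether the issue arises in practice.

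The cost is one sentence and a small programming change using times already recorded. Response rates may come out slightly lower. Subjects imputed for site closure are scored on fixed 7-day steps and are not affected.

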#### 4 LIST OF ABBREVIATIONS

| Abbreviation | Definition   |
|--------------|--|
| AE           | adverse event                                      |
| CFR          | Code of Federal Regulations                        |
| DECT         | dual-energy computed tomography                    |
| DMC          | data monitoring committee                          |
| ECG          | Electrocardiogram                                  |
| eCRF         | electronic case report form                        |
| FDA          | Food and Drug Administration                       |
| G6PD         | glucose-6-phosphate dehydrogenase                  |
| GCP          | Good Clinical Practice                             |
| HAQ          | Health Assessment Questionnaire                    |
| HAQ-DI       | Health Assessment Questionnaire – Disability Index |
| ICF          | informed consent form                              |
| ICH          | International Council for Harmonisation            |
| IMM          | Immunomodulator                                    |
| IND          | Investigational New Drug                           |
| IR           | infusion reaction                                  |
| IRB          | Institutional Review Board                         |
| IV           | intravenous(ly)                                    |
| miITT        | modified intention-to-treat                        |
| MTX          | Methotrexate                                       |
| NSAID        | non-steroidal anti-inflammatory drug               |
| PK           | pharmacokinetic(s)                                 |
| PO           | oral   |
| PBMC         | peripheral blood mononuclear cell                  |
| RNA          | ribonucleic acid                                   |
| RTSM         | Randomization and Trial Supply Management          |
| SAE          | serious adverse event                              |
| SAP          | statistical analysis plan                          |
| sUA          | serum uric acid                                    |
| ULT          | urate lowering therapy                             |
| USP          | United States Pharmacopeia                         |

Note: Abbreviations used only once in a paragraph or in tables or figures are defined within the relevant paragraph, table, or figure.

